8.3. Clinical Laboratory Evaluations

The planned summaries for clinical laboratory evaluations are provided in [Table JAHW.8.3](#) and are described more fully in compound level safety standards and in the laboratory-related PHUSE white papers (PHUSE Computational Science Deliverables Catalog WWW; PHUSE Computational Science Deliverables Catalog WWW).

Table JAHW.8.3. Summary Tables Related to Clinical Laboratory Evaluations

Analysis	Population or Analysis Set ^a
Spaghetti plots for observed values	A, L
Listing of abnormal findings for laboratory analyte measurements, including qualitative measures	Enrolled

^a Analysis Sets are abbreviated as follows: A = Part A safety population, L = Long-term.

8.4. Vital Signs, Growth and Other Physical Findings

The planned summary analyses and by-patient listing for vital signs (systolic blood pressure [BP], diastolic BP, pulse) and other physical findings (weight, body mass index [BMI], temperature, height, head circumference) will be provided for the safety population and are summarized in [Table JAHW.8.4](#). The reference limits for pulse/heart rate (P/HR) and blood pressure parameter will align with Lilly cardiovascular safety advisory committee's guidance "Reference Limits for PR/HR, BP, Orthostasis, & ECG Parameters" [CCI](#)

Table JAHW.8.4. Summary Tables Related to Vital Signs

Analysis	Population or Analysis Set ^a
Spaghetti plots for observed values	A, L
Listing of abnormal finding in pulse/heart rate and blood pressure.	Enrolled

^a Analysis Sets are abbreviated as follows: A = Part A safety population, L = Long-term.

The reference limits for abnormal finding in pulse/heart rate and blood pressure is listed in [Table JAHW.8.5](#).

Table JAHW.8.5. Reference Limits for Blood Pressure, Pulse/Heart Rate

Age (years)		Systolic BP, mm Hg (supine or sitting forearm at heart level)	Diastolic BP, mm Hg (supine or sitting forearm at heart level)	Pulse/HR bpm (supine or sitting)
Infant <2	Low	≤ 70 and decrease ≥ 15	≤ 35 and decrease ≥ 10	<70 and decrease ≥ 25
	High ^a	≥ 108 and increase ≥ 15	≥ 74 and increase ≥ 10	>190 and increase ≥ 25
Child 2-4	Low	≤ 75 and decrease ≥ 15	≤ 40 and decrease ≥ 10	<60 and decrease ≥ 25
	High ^a	≥ 110 and increase ≥ 15	≥ 76 and increase ≥ 10	>160 and increase ≥ 25
Child 5-9	Low	≤ 80 and decrease ≥ 15	≤ 45 and decrease ≥ 10	<60 and decrease ≥ 25
	High ^a	≥ 119 and increase ≥ 15	≥ 78 and increase ≥ 10	>150 and increase ≥ 25
Child 10-12	Low	≤ 85 and decrease ≥ 20	≤ 50 and decrease ≥ 10	<60 and decrease ≥ 25
	High ^a	≥ 126 and increase ≥ 20	≥ 82 and increase ≥ 10	>140 and increase ≥ 25
Adolescent >13	Low	≤ 90 and decrease ≥ 20	≤ 50 and decrease ≥ 10	<50 and decrease ≥ 15
	High ^a	≥ 129 and increase ≥ 20	≥ 86 and increase ≥ 10	>120 and increase ≥ 15
Adult ≥ 18	Low	≤ 90 and decrease ≥ 20	≤ 50 and decrease ≥ 10	<50 and decrease ≥ 15
	High ^a	≥ 129 and increase ≥ 20	≥ 90 and increase ≥ 10	>100 and increase ≥ 15

Abbreviations: BP = blood pressure; HR = heart rate.

^a The high limit values shown in this table correspond to 95th percentile for the age group under the 2017 ACC/AHA Task Force on Clinical Practice Guidelines revised criteria for hypertension. Values higher than 95th percentile are consistent with Stage 1 or Stage 2 hypertension. Under some circumstances it may be appropriate to conduct analyses considering only the change from baseline reference limit.

Source: Flynn et al. 2017; Whelton et al. 2018.

Standardized Growth

Weight, height, BMI and head circumference data will be merged to the Centers for Disease Control and Prevention (CDC) standard growth data (released in 2000) by age and gender in order to compare patients' growth with the standard. Z-score and standardized percentile of weight, height, and BMI at each visit will be calculated and compared to the 2000 CDC growth charts.

The z-score and percentile calculations are based on algorithms and data provided by the National Center for Health Statistics. The data are provided in the CDC website (CDC resources page WWW).

The summaries will be provided and patients' mean of the parameter of interest will be plotted versus investigational product exposure time. By-patient listings of actual measures will be provided if needed.

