6.1. Inclusion Criteria

Patients are eligible to enroll in the study only if they meet all of the following criteria at screening and at baseline:

Patient and Disease Characteristics

- [1] Are at least 2 years and less than 18 years of age; full date of birth will be collected except in countries in which it is not allowed.
- [2] Have a diagnosis of JIA-U or chronic ANA-positive uveitis without systemic features.
- [3] Have active anterior uveitis, defined as cellular infiltrate in the anterior chamber of SUN criteria grade $\geq 1+$ at Visit 1 (screening) and Visit 2 (potential randomization), despite prior treatment with adequate doses of topical steroid therapy and MTX.
- [4] Have an inadequate response or intolerance to MTX (minimum dose of 10 mg/m²/week, with a maximum dose of 25 mg/m²/week). Patients considered to have inadequate response must have received MTX for at least 12 weeks before an inadequate response may be determined, and must have been on a stable dose for at least 4 weeks prior to screening if continuing MTX therapy during the study.
- [5] Are receiving topical corticosteroid eye drops at a stable dose for at least 2 weeks prior to screening (maximum of 4 drops/day per eye at screening).

Informed Consent

- [6] Both a parent or legal guardian and the patient (as appropriate) are able to understand and fully participate in the activities of the study and sign their consent and assent, respectively, in accordance to local guidelines.

Contraception

- [7] Male or nonpregnant, nonbreastfeeding female patients

Patients of child-bearing potential who are abstinent (if this is complete abstinence, as their preferred and usual lifestyle) must agree to remain abstinent.

Total abstinence is defined as refraining from intercourse during the entirety of the study and for at least 1 week following the last dose of investigational product. Periodic abstinence such as calendar, ovulation, symptothermal, postovulation methods and withdrawal are not acceptable methods of contraception.

Otherwise, patients and their partners of child-bearing potential must agree to use 2 effective methods of contraception, where at least 1 form is highly effective for the entirety of the study and for at least 1 week following the last dose of investigational product.

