10.3.4.3. Vital Signs, Physical Findings, and Other Safety Evaluations

Vital signs will be presented as mean changes from baseline and as incidence of abnormal values. Other data, including body weight and height data will be summarized. Weight, height, and BMI data will be merged to the Centers for Disease Control standard growth data by age and gender to compare subjects' growth with the standard. Other measures related to growth velocity (e.g., occipital circumference measurement) will be evaluated. Further analyses may be performed.

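### As printed, SAP Table JAHW.8.5 has no blood pressure or pulse limits for age 13, and two overlapping sets from age 18

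*SAP*

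**What the plan says.** SAP Section 8.4 plans two displays in Table JAHW.8.4. One is "Spaghetti plots for observed values", for Part A and the long term. The other is "Listing of abnormal finding in pulse/heart rate and blood pressure", for enrolled patients. The SAP ties the second to Table JAHW.8.5: "The reference limits for abnormal finding in pulse/heart rate and blood pressure is listed in" that table. Its age rows are under 2, 2-4, 5-9, 10-12, "Adolescent >13" and 18 or over. Each row gives a threshold and a minimum change for high and low values.

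On where the limits come from, the SAP says: "The reference limits for pulse/heart rate (P/HR) and blood pressure parameter will align with Lilly cardiovascular safety advisory committee's guidance". That guidance is an internal sponsor document that the SAP does not reproduce, and the text directly after the reference is redacted.

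Protocol Section 6.1 admits patients who "Are at least 2 years and less than 18 years of age". Protocol Section 10.3.4.3 adds a further use for such limits: "Vital signs will be presented as mean changes from baseline and as incidence of abnormal values". Neither document gives other limits for age 13 or a rule for an age that fits no row or two rows.

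**The concern.** Table JAHW.8.5 is an operative rule. It decides who appears in a planned safety listing, and it is the only definition of an abnormal vital sign in either document. If it is programmed as printed, a 13-year-old's reading has nothing to be compared with. It drops out without a message, because a missing limit looks the same as a normal result. A patient aged 18 or over has two sets of limits, and the result then depends on the order in which the program tests the rows. In either case the choice would be made in code and not recorded in the SAP.

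**Working it through.** The plan states no figure to reproduce. The check assigns each possible age to the printed rows.

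**Inputs.** The age bands are from SAP Table JAHW.8.5. Entry age is 2 to under 18 (Protocol Section 6.1). Treatment is 24 weeks in Part A plus 260 in Part B, which is 284 weeks: 284 × 7 / 365.25 = 5.44 years. The highest age on treatment is therefore just under 18 + 5.44 = 23.4, so whole-year ages 2 to 23 are needed.

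**Age in completed years.**
- 2 to 12: one row each
- 13: no row
- 14 to 17: one row each
- 18 to 23: two rows (adolescent and adult)

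**Age as a decimal.** Ages 13.01 and 13.5 now fall in the adolescent row, but 4.5, 9.5, 12.5 and exactly 13.0 fall in none. The bands 2-4, 5-9 and 10-12 adjoin only in completed years, so that must be the intended reading. On it, 13 is the only uncovered age in the eligible range.

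**Do the neighbouring rows differ?** Each cell shows the threshold, then the minimum change.

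| Limit | 10-12 | Adolescent | Adult |
|---|---|---|---|
| High systolic (mm Hg) | ≥126, 20 | ≥129, 20 | ≥129, 20 |
| High diastolic (mm Hg) | ≥82, 10 | ≥86, 10 | ≥90, 10 |
| High pulse (bpm) | >140, 25 | >120, 15 | >100, 15 |
| Low systolic (mm Hg) | ≤85, 20 | ≤90, 20 | ≤90, 20 |
| Low diastolic (mm Hg) | ≤50, 10 | ≤50, 10 | ≤50, 10 |
| Low pulse (bpm) | <60, 25 | <50, 15 | <50, 15 |

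- At 13, a pulse of 130 after a rise of 25 is abnormal on the adolescent row and not on the 10-12 row. The gap cannot be filled from either side without consequence.
- At 18, a diastolic of 87 after a rise of 10 is abnormal on the adolescent row and not on the adult row.
- At 18, a pulse of 110 after a rise of 15 is abnormal on the adult row and not on the adolescent row.

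**Which date is age taken at?** Section 8.4 does not say. If age is fixed at entry, a child who enters at 13 matches no row for the whole study, and the overlap never arises because entry is below 18. If age is taken at each visit, the gap lasts for the year at 13. It then also reaches children who enter from about 13 − 5.44 = 7.6 years and stay long enough, and the overlap arises for those who turn 18. Protocol Section 7.4 expects some patients to pass 18 in Part B.

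**Illustrative share.** There are 16 eligible whole-year ages (2 to 17), so 1/16 = 6.25% of patients would enter at 13 if entry ages were evenly spread. The documents give no age distribution.

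**After relabelling.** With the adolescent row read as 13 to under 18, every whole-year age from 2 to 23 falls in exactly one row.

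**The case against.** The strongest reply is that this is a sign slip that any programmer would query. The row follows a band ending at 12, so ≥13 is the natural reading. The documents show similar slips: the tablet rule is printed with ≥12 in the SAP's Figure 5.1 note and Section 5.3, but with >12 in its Figure 5.2 note and in Protocol Section 7.2. The governing limits also sit in sponsor guidance that may cover age 13. At 18, the adult row is the more specific one and would naturally take precedence; only two of the six limits differ. Most of this stands. It shows that the correction is small, but it does not supply the rule, which the SAP should state.

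A reader might infer something stronger: that abnormal vital signs in 13-year-olds go unseen, because vital signs are reported only in the plots and this listing. The documents do not support that.
- The plots show observed values without using the limits.
- SAP Section 6.1.3 plans summaries by treatment group, and Protocol Section 10.3.4.3 plans mean changes from baseline.
- SAP Section 10 gives the data monitoring committee summaries of high and low vital signs, without saying which limits apply.
- Under Protocol Section 9.4.2, clinically significant findings that lead to a diagnosis are reported as adverse events.

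Nor does the 6% figure measure missed findings. It counts patients under an assumed age spread, and an entry in the listing needs both a threshold breach and a sufficient change.

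**Conclusion.** The gap and the overlap are both real in the printed table. Read literally in completed years, it leaves 13-year-olds out of the listing of abnormal pulse and blood pressure findings and out of any abnormal-value counts built on the same limits. It also classifies patients aged 18 and over ambiguously on high diastolic pressure and high pulse, if age is taken at the visit.

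This is a minor defect of safety display, probably a slip for ≥13. It does not touch the primary analysis, eligibility or patient management. The number of findings affected cannot be estimated from the documents. The conclusion assumes that the bands are in whole years, as the lower rows require. It concerns the printed table and makes no claim about what the unseen guidance says.

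**What to change.** Check the band edges of Table JAHW.8.5 against the sponsor reference-limit guidance that Section 8.4 cites. Then relabel the adolescent row, presumably as 13 to under 18, so that every age falls in exactly one row. Add a sentence stating that age is in completed years and whether it is taken at baseline or at the visit. The cost is one table cell and one sentence in the SAP, with no change to data collection.

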5.1.3. Open-Label Treatment Period – Part B

Part B is an open-label extension period. In the previous study design (amendment d or prior), all patients who were receiving baricitinib in Part A received oral baricitinib once daily for approximately 260 weeks. Patients who were randomized to adalimumab treatment in Part A continued to receive adalimumab for approximately 96 weeks in Part B and were then switched to baricitinib for the remaining weeks. The first dose of baricitinib was given approximately 2 weeks after the last injection of adalimumab.

Since then, the protocol and study design has been modified (Amendment e). Patients receiving adalimumab will be discontinued from the study after Week 24.

Patients currently assigned to baricitinib who have completed the primary endpoint as a responder will continue receiving baricitinib until the end of study or discontinuation from the study. Investigator may consult the study team for guidance on study continuation in the event the patient is a nonresponder at the primary endpoint, but demonstrates clinically meaningful benefit from baricitinib.

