10.3.4.2. Clinical Laboratory Tests

All clinical laboratory results will be descriptively summarized. Individual results that are outside the normal reference ranges will be flagged in data listings. Quantitative clinical hematology, chemistry, and urinalysis variables obtained at the baseline to postbaseline visits will be summarized as changes from baseline. Categorical variables, including the incidence of abnormal values and incidence of AEs of special interest, will be summarized by frequency and percentage of patients in corresponding categories. Shift tables will be presented for selected measures.

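### Growth is reported as a mean level against exposure time with no within-patient change, and SAP Tables 8.3 and 8.4 omit the change-from-baseline summaries that the protocol specifies

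*SAP*

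**What the plan says.** **Growth.** SAP 8.4 (Standardized Growth) states: "Z-score and standardized percentile of weight, height, and BMI at each visit will be calculated and compared to the 2000 CDC growth charts". Patients' "mean of the parameter of interest will be plotted versus investigational product exposure time". It also promises summaries without describing them, and adds: "By-patient listings of actual measures will be provided if needed". It does not define the plotted parameter (z-score or percentile is the natural reading), the set of children behind each point, or any change from baseline. Protocol 10.3.4.3 says that height and weight will be summarised and compared with the CDC standard, and that measures related to growth velocity will be evaluated.

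**Who is observed later.** Protocol 5.1.3, as amended by (e): "Patients currently assigned to baricitinib who have completed the primary endpoint as a responder will continue receiving baricitinib until the end of study", or until discontinuation. For a nonresponder with clinically meaningful benefit, the investigator may consult the study team about continuing. Under Amendment (d) or earlier, all baricitinib patients continued. SAP Table 8.1 ends the long-term baricitinib window at the data cut or up to 30 days after the last dose.

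**Vital signs and laboratory values.** Protocol 10.3.4.3: "Vital signs will be presented as mean changes from baseline and as incidence of abnormal values". Protocol 10.3.4.2: "Quantitative clinical hematology, chemistry, and urinalysis variables obtained at the baseline to postbaseline visits will be summarized as changes from baseline". SAP Tables 8.3 and 8.4 each contain two rows: "Spaghetti plots for observed values", and a listing of abnormal findings.

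**The concern.** Growth is a named safety topic. Protocol 8.2 gives clinically meaningful adverse growth trends, in an individual or an age group, as a possible reason for discontinuation, and Protocol 9.4.6.2 sets up growth monitoring. A mean level at each exposure time answers the growth question cleanly only if the same children stand behind every point. If the set changes after Week 24, the curve mixes who stayed with how they grew, and it can understate or exaggerate a trend. With about 20 to 30 baricitinib children, a few departures can matter.

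The vital-sign and laboratory issue is different and needs no assumption about drop-out: the protocol specifies summaries that the SAP tables do not list.

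**Working it through.** **1. The plan's own figure.** The documents give no growth figure. The one usable planning figure is 20 responders out of 30 (Protocol 10.1, original sample size). With the Beta(1,1) prior, 20/30 gives Beta(21,11) and P(response rate > 57%) = 0.848, in line with the stated greater than 80%. It implies 10/30 = 0.333 nonresponders, used below as an upper planning value for the share that leaves. The documents do not say how many will leave.

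**2. Composition shift.** Let a share s leave, with a baseline mean z that is d below that of the stayers.

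- Baseline mean of all = stayers' mean − s × d
- Later mean with no growth change = stayers' mean
- Shift = s × d
- Apparent change when every child truly loses 0.25 z = s × d − 0.25

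The gap d and the 0.25 z loss are assumed.

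| Share leaving | d = 0 | d = 0.3 | d = 0.5 | d = 0.75 | d = 1.0 |
|---|---|---|---|---|---|
| 1/3 | −0.25 | −0.15 | −0.08 | 0.00 | +0.08 |
| 0.20 | −0.25 | −0.19 | −0.15 | −0.10 | −0.05 |
| 0.10 | −0.25 | −0.22 | −0.20 | −0.175 | −0.15 |

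If leavers started taller (d below 0), the same term exaggerates the loss. Mean within-patient change in the stayers is −0.25 in every cell.

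**3. Precision with no systematic gap.** Assume z-score SD 1, 30 children at baseline and 20 staying. With within-child correlation 0.9, the change SD is √(2 × 0.1) = 0.447; change is taken as independent of baseline.

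- Chance gap between 20 stayers and 10 leavers: SD √(1/20 + 1/10) = 0.387, so the shift has SD 0.387/3 = 0.129
- SE of the apparent change: √(0.129² + 0.2/20) = √(0.0167 + 0.0100) = 0.163
- SE of the mean within-patient change: √(0.2/20) = 0.100

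A 20,000-run simulation gave 0.163 and 0.100. If the SD is instead held at 1 at both times with correlation 0.9, the first SE is √(1/20 + 1/30 − 2 × 0.9/30) = 0.153, and the conclusion is the same. In the simulation, a true 0.25 z loss showed no fall in the plotted mean in 6% of runs at d = 0, 31% at d = 0.5 and 51% at d = 0.75. The within-patient figure was about 0.6% throughout.

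**4. Protocol against SAP tables.**

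| Domain | Protocol | SAP Table 8.3 or 8.4 | Partial cover elsewhere in the SAP |
|---|---|---|---|
| Laboratory | Change from baseline | Spaghetti plots, listing | Baseline-to-maximum shift tables for hematology, lipids, creatinine and CPK; hepatic thresholds by baseline level |
| Vital signs | Mean change from baseline; incidence of abnormal values | Spaghetti plots, listing | BP and pulse limits in Table 8.5 that require a change as well as a threshold |

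The partial cover does not supply a mean change for either domain, and no table gives the incidence of abnormal vital signs. The SAP version history neither records nor explains the difference.

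**The case against.** The strongest reply is that within-patient information is already planned. A spaghetti plot draws one line per child, and the text introducing Table 8.4 covers height, weight, BMI and head circumference and promises summary analyses. SAP 6.1.3 says that vital signs, body weight and laboratory variables will be summarised by group. Shift tables and change-based limits exist, SAP 8.3 refers to compound-level standards that are not available here, and Protocol 9.4.6.2 has the DMC review growth changes for individuals and groups.

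Much of this stands. A reader might infer that the plan holds no within-patient content at all; the documents contradict that. The reply does not fully answer the point, for four reasons:

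- The spaghetti plots show observed values. Raw height rises in a growing child even while the z-score falls, so they are a weak display of growth deficit.
- The shift tables and change-based limits do not cover growth.
- SAP 6.1.3 does not say that change from baseline will be summarised.
- DMC review is monitoring, not the reported analysis.

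The compound-level standards might contain the missing laboratory summaries. That cannot be checked, and Table 8.3 should say so if they do.

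It is also fair that Protocol 10.3.1 lets analysis methods change without an amendment unless a principal feature is affected. It still requires the change and its justification to appear in the clinical study report. For growth, the protocol does not itself promise change from baseline, so that half concerns choice of method, not a contradiction.

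**Conclusion.** The point holds in two parts of modest size.

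**Growth.** A mean level against exposure time is open to shifts in who is observed, and it is less precise than mean within-patient change: SE about 0.16 against 0.10, a ratio of about 1.6, under the assumptions in the working. Comparing the SE of a mean level with the SE of a mean change would overstate the gain; the two figures here both refer to change over time.

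Two stronger readings are tempting and not supported. A reader might infer that most nonresponders leave at Week 24 by design. No document says so: earlier amendments kept every baricitinib patient, and Amendment (e) leaves room for exceptions. A reader might also infer that the plot will hide a growth loss. Full masking of 0.25 z needs a particular combination, such as one third leaving with a 0.75 z deficit at baseline. Nothing in the documents links uveitis nonresponse to height, and the effect could run either way.

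**Vital signs and laboratory values.** Tables 8.3 and 8.4 do not list summaries that Protocol 10.3.4.2 and 10.3.4.3 specify. This rests on the text alone, with partial cover from the shift tables and change-based limits.

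**What to change.** In SAP 8.4, make the growth summary and plot the mean within-patient change from Part A baseline in height, weight and BMI z-score at each visit, in children with both values, with n shown at every point. SAP 6.1.2 already defines that baseline.

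This removes shifts caused by baseline composition. It does not remove selection if the children who leave are those losing growth, and the SAP should say so.

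In Tables 8.3 and 8.4, restore the change-from-baseline summaries for laboratory values and vital signs and the incidence of abnormal vital signs. Any that are deliberately dropped should be recorded with the reason, as Protocol 10.3.1 requires.

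The cost is SAP wording and a few additional standard tables from data already collected.
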